that incisions are covered with a postsurgical cover dressing, for up to a period of 48 hours, to help control postoperative bleeding, absorb exudate, provide mechanical protection, help to reduce edema and provide protection from exogenous sources (Mangram *et al* 1999). Multiple patient comorbidities, environmental factors and the type and length of surgery may elevate certain groups of patients into a higher level of risk of developing a post-surgical complication: calling for a higher degree of vigilance and postsurgical intervention. Surgical complications include; wound dehiscence, infection (deep or superficial), hematomas, seromas, tissue necrosis and delayed incision healing. Complication rates can range from 19% in patients requiring open reduction and internal fixation (ORIF) of tibial plateau, pilon and calcaneus fractures (Stannard *et al* 2011) up to 50% in high energy trauma wounds (Stannard *et al* 2006). These complications can have a high degree of morbidity for the patient and further sequelae may result in additional surgical procedures or revisions, a lower functional status for the patient, an increased in length of hospital stay (LOS) and a higher cost for the healthcare provider.

Traditional NPWT has been shown to be an effective adjunct therapy in the treatment of acute and chronic wounds, but the emergence of incisional NPWT (iNPWT) and supporting evidence is growing momentum. *In vitro* studies have shown that iNPWT may help to improve the stimulation of blood flow, help manage exudate, help to reduce edema, provide a mechanical and “splinting” effect on the incision and provide mechanical protection from the environment. Its impact on the prevention or reduction of post-surgical incision complications is still in its infancy, but recent studies pioneered by Stannard *et al* (Stannard 2011) have been encouraging and have demonstrated a statistically significant reduction in infection and dehiscence in patients considered as high-risk following severe skeletal trauma.

The aim of this study is to assess the prevention of incision healing complications in patients undergoing KA and THA treated with either Single-Use Incisional NPWT compared to standard of care dressings.

PRIMARY OBJECTIVE

Compare PICO wound dressing to current MOI standard of care for postoperative incision management in Knee Arthroplasty (KA) or Total Hip Arthroplasty (THA) patients.

Outcome Measures:

- Primary: Incision appearance at 1, 2 and 5 weeks postop

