- VAS (Incision Healing Assessment Form) 0-10 continuous, based on standardized digital image (1 week) and exam (2 and 5 weeks). The VAS can be completed by the PI, any of the sub-investigators, or any properly trained physicians or RN associated with the project. If the VAS is completed based on an incisional photo, study staff will collect the exact date the photo was taken.
- If the subject will not be returning 2 weeks postoperatively as standard of care, they will be asked to take another standardized digital image at 2 weeks, and the 2 week follow-up will be done over the phone.

SECONDARY OBJECTIVES

To assess complications between patients treated with either PICO or standard care dressings. **Outcome Measures:**

- Secondary: Daily phone calls for first week; follow-up appointments
 - Drainage amount
 - User-friendliness for patient
 - Complications
 - Return to OR
 - Need for antibiotics

Data Analysis:

- Compare TOTAL PICO vs. SOC incision appearance VAS and drainage amount using t-Test
- Compare Primary JA (joint arthroplasty) PICO vs. SOC incision appearance VAS and drainage amount using t-Test
- Compare Revision JA PICO vs. SOC incision appearance VAS and drainage amount using t-Test
- Compare TOTAL PICO vs. SOC for all other outcome measures using chi-square based on number in each category
- Compare Primary JA PICO vs. SOC for all other outcome measures using chi-square based on number in each category
- Compare Revision TJA PICO vs. SOC for all other outcome measures using chi-square based on number in each category
- Post-hoc assessment of risk factors – ASA level, surgeon, BMI

EVALUATION DESIGN

The study will comprise a prospective, open labeled, single-centre study to determine the efficacy of a Single-Use Negative Pressure Wound Therapy (NPWT) System (PICO) in the prevention of postsurgical incision healing complications in patients undergoing KA and THA. The study will be comparative and randomized according to a pre-determined randomization schedule. The study will be open-labeled due to the physical appearance of both the investigational product and standard dressings, which will be impossible to blind to both the investigator and/or patient. Patients will be stratified according to the type of surgical procedure (KA/THA) and primary or revision procedure. Patients will be followed up for a period of 5 weeks, to determine if there are any latent problems with infection or dehiscence.

PICO

IRB Project # 1208434

Version 8

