24MAR2016

NUMBER OF PATIENTS

1000 patients will be enrolled into the evaluation.

INCLUSION CRITERIA

- 1 – Patient ≥ 18 years old
- 2 - Male or non-pregnant females
- 3 – Patient is scheduled to have a surgical procedure for Knee Arthroplasty (either total knee arthroplasty or unicompartmental knee) or Total Hip Arthroplasty. May be Primary or Revision Procedure.
- 4 - The patient is able to understand the trial and is willing to consent to the trial

EXCLUSION CRITERIA

- 1 – Patients who in the opinion of the investigator may not complete the study for any reason
- 2 - Patients with a known history of poor compliance with medical treatment
- 3 - Patients who have participated in this trial previously and who were withdrawn
- 4 - Patients with known allergies to product components (silicone adhesives and polyurethane films (direct contact with wound), acrylic adhesives (direct contact with skin), polyethylene fabrics and super-absorbent powders (polyacrylates) (within the dressing)
- 5 – Patients not capable of obtaining a standardized digital picture and submitting it to the site.

ASSIGNING PATIENTS TO TREATMENT

Patients who meet all the inclusion criteria will be randomized to treatment according to a pre-determined randomization schedule. Randomization method will be [1:1](#), PICO versus standard postsurgical dressings, taken from a pre-assigned randomization table. The patient will be randomized to the application of either PICO or standard postsurgical dressings. If a patient is having a bilateral procedure, they will receive the same dressing treatment on both sides.

TREATMENT REGIME

Patients will be assessed against the eligibility criteria to determine their suitability for inclusion in the study.

Pre-Trial	
Investigator discusses study with the patient and provides the patient with a Patient Consent Form
 
Patient provides written consent to participate in the study
 
Patient functionality and QoL (quality of life) assessment (SF12)

Day 0	
Patient provides written consent to participate in the study (if not done prior to day 0)
 
Complete eligibility checklist, relevant medical history and concomitant medication
 
Patient functionality and QoL (quality of life) assessment (SF12) (*if not done at Pre-Trial visit)
 
ASA level
 
BMI
 
Operative procedure (KA or THA)
 
Incision assessment following procedure
 
First dressing application

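### The plan stratifies patients by KA/THA and primary/revision, but the overall PICO versus standard-care tests adjust for neither; adjusting costs almost nothing and may gain a little precision.

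*Combined protocol and SAP*

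**What the plan says.** The Evaluation Design section states: "Patients will be stratified according to the type of surgical procedure (KA/THA) and primary or revision procedure". The inclusion criteria admit both kinds of procedure ("May be Primary or Revision Procedure"). The primary outcome is "Incision appearance at 1, 2 and 5 weeks postop", scored on a 0-10 VAS.

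Under Data Analysis, the overall comparisons are:

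- continuous outcomes: "Compare TOTAL PICO vs. SOC incision appearance VAS and drainage amount using t-Test";
- the rest: "Compare TOTAL PICO vs. SOC for all other outcome measures using chi-square based on number in each category".

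The same tests are then repeated separately in primary and in revision patients, for example "Compare Revision JA PICO vs. SOC incision appearance VAS and drainage amount using t-Test". KA/THA does not appear in the list. The only other factors named are ASA level, surgeon and BMI, and those are post hoc.

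Assigning Patients to Treatment describes 1:1 allocation, "taken from a pre-assigned randomization table", and names no strata.

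**The concern.** A trial that stratifies by two factors would normally carry them into the main comparison. Here the overall tests do not, and the subgroup tests by primary/revision do not adjust the overall result.

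What is at stake depends on the randomisation table:

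- **Balanced within strata.** The design has already removed between-stratum differences from the treatment contrast. The t-test still counts them as noise, so if the strata predict outcome its interval is too wide and its error rate falls below 5%. The adjusted and unadjusted estimates are then nearly the same; adjustment corrects the standard error.
- **Not balanced within strata.** The t-test keeps its 5% error rate, but chance imbalance adds variance that adjustment would remove. This is a true gain in precision.

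The documents do not settle which case applies. In neither case is the result biased or the false-positive rate raised.

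**Working it through.** **Inputs from the documents.** 1000 patients, 1:1; two binary stratification factors; t-test and chi-square for the overall comparisons. The 1000 cannot be reproduced, because no alpha, power, SD or target difference is given.

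**Assumptions.** Two-sided alpha 0.05, 500 per arm, no dropout. R2 is the share of VAS variance explained by the strata. Under these assumptions the smallest difference with 80% power is (1.96 + 0.84) × sqrt(2/500) = 0.177 SD when R2 = 0.

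**Plausible R2.** With revision share r, KA share k, and revision and hip effects in SD units, v = r(1−r)·rev² + k(1−k)·hip² and R2 = v/(1+v). For r = 5-20% and k = 50-70%:

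- both effects 0.25 SD: R2 = 1.6-2.5%;
- both effects 0.5 SD: R2 = 6.0-9.3%;
- revision effect 0.25 SD, no hip effect: R2 = 0.3-1.0%.

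**VAS, closed form.** The true difference is set so that the adjusted analysis has 80% power: 2.80 × sqrt((1−R2) × 2/500), or 0.177, 0.175, 0.173 and 0.168 SD at R2 = 0, 2, 5 and 10%.

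- Equivalent N = 1000/(1−R2).
- Balanced: interval excess = 1/sqrt(1−R2) − 1; type I error = 2·P(Z > 1.96/sqrt(1−R2)); power = P(Z > 1.96/sqrt(1−R2) − 2.80).
- Not balanced: type I error 5%; power = P(Z > 1.96 − 2.80·sqrt(1−R2)).

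| R2 | Equivalent N | Interval excess (balanced) | t-test type I error (balanced) | t-test power (balanced) | t-test power (not balanced) |
|---|---|---|---|---|---|
| 0 | 1000 | 0% | 5.0% | 80.0% | 80.0% |
| 2% | 1020 | 1.0% | 4.8% | 79.4% | 79.2% |
| 5% | 1053 | 2.6% | 4.4% | 78.5% | 78.0% |
| 10% | 1111 | 5.4% | 3.9% | 76.9% | 75.7% |

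When power is already high the difference nearly vanishes. At 0.25 SD, 0.25/sqrt(2/500) = 3.95; with R2 = 10%, power is 98.6% adjusted against 98.2% (balanced) or 97.7% (not balanced).

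**VAS, simulation.** 20,000 runs, with assumed strata of 510 primary KA, 340 primary THA, 90 revision KA and 60 revision THA, and a linear model with both factors. Results at R2 = 0, 2, 5 and 10%:

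- Balanced: t-test type I error 5.1, 4.6, 4.3 and 3.9%, against 4.8-5.1% adjusted; power 80.0, 79.6, 78.7 and 77.3%, against 80.0-80.3%.
- Not balanced: t-test type I error 4.8-5.1%; power 79.5, 79.1, 77.8 and 75.7%, against 79.5-80.0%.

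**Cost when R2 = 0.** The unbalanced simulation gives a standard-error ratio (t-test to adjusted) of 0.999, a cost of about 0.1% with two added terms. With all four strata (three terms) it is about 0.15%.

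**Binary outcomes, simulation.** 200,000 runs, same strata. Control rates are in the stratum order above; RR is the risk ratio. Power is chi-square against Cochran-Mantel-Haenszel (CMH).

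| Control rates | RR | Balanced | Not balanced |
|---|---|---|---|
| 5/5/10/10% | 0.40 | 81.42 vs 81.47 | 81.47 vs 81.55 |
| 8/10/16/20% | 0.53 | 80.61 vs 80.95 | 80.55 vs 80.90 |
| 6/10/25/40% | 0.55 | 81.33 vs 83.05 | 80.57 vs 82.71 |
| 2/2/4/4% (sparse) | 0.13 | 84.62 vs 84.75 | 84.66 vs 85.51 |
| 1/1/3/5% (sparse) | 0.20 | 49.95 vs 50.29 | 50.15 vs 51.50 |

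The gain is 0.05 to 2.1 points. CMH type I error was 4.8-5.0% throughout, and coverage of the Mantel-Haenszel risk-difference interval was 93.8-95.2%.

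**The case against.** The strongest reply is that this is optional. The planned tests are valid, no conclusion is put at risk, and nothing in the documents shows that the strata predict VAS: the background says only that type of surgery may raise complication risk. The 10% end of the R2 range needs half-SD effects of both factors. With a 0.25 SD revision effect alone, R2 is 0.3-1.0%, worth 3 to 10 patients on 1000, and t-test power is 79.6-79.9% against 80%. All of this stands, and it limits the size of the point.

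The sparse binary gains are also weak evidence. With a 2% control rate in every stratum, so that there is nothing to adjust for, CMH still shows 79.4% against 78.6% at RR 0.13 without balance. Most of the 0.8-point gain in the 2/2/4/4% case is therefore discreteness of the tests. The 2-point gain does not depend on the sparse cases, but it needs control rates spread from 6 to 40%.

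Finally, primary/revision is not ignored, and the stratification sentence might describe the subgroup analyses rather than the randomisation. That is fair, but it leaves KA/THA unused and does not adjust the overall comparison. It is also a reason to clarify the text. None of these replies argues for leaving out a nearly free adjustment.

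**Conclusion.** The concern holds as a precision and consistency point, not as an error. The overall tests use neither stratification factor, and no other section supplies the adjustment. The gain ranges from nil, if the strata are not prognostic, to about 3 power points (balanced) or 4 (not balanced) for VAS at R2 = 10% and 80% adjusted power. It is under 1 point when power is already high and about 0 to 2 points for binary outcomes. These sizes rest on assumed alpha, stratum shares and prognostic strength. That the cost is negligible does not depend on the assumed prognostic strength.

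**What to change.** - **VAS and drainage, overall comparison.** Use a linear model with treatment, KA/THA and primary/revision, fitted to VAS at each of weeks 1, 2 and 5 and to drainage.
- **Categorical outcomes, overall comparison.** For complications, return to OR, need for antibiotics and the user-friendliness items asked in both arms, use a CMH test stratified by the same two factors, in its generalised form where there are more than two categories. Add a Mantel-Haenszel risk difference for binary outcomes; it tolerates sparse revision strata.
- **Keep** the unadjusted tests as sensitivity analyses and the primary and revision subgroup tests as planned.
- **Reconcile** Evaluation Design with Assigning Patients to Treatment by stating whether the randomisation table is stratified by these two factors.

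The cost is some rewording of Data Analysis and one sentence in the assignment section. No new data are needed: KA or THA is recorded on Day 0, and the plan already splits its analyses by primary/revision. How the two incisions of a bilateral patient enter the analysis is a separate matter and needs its own rule under either approach.

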Days 1-7 (following surgery)	
Daily communication with the subject (in person or phone contact) to collect the following information:
 
○ Drainage amount○ User-friendliness for subject (including ease of use and subject's opinion of the noise associated with the PICO device.○ Assessment of Complications○ Assessment of return to OR○ Assessment of need for antibiotics

	
*On the days within this window that fall on a weekend or holiday, the subject will not be contacted, but rather asked for a summary of this information on the next business day. If the subject is unreachable despite the site's best effort for one or a number of the days in this window, the subject will be asked to give a summary of the "missed" days.

Day 7 (1 week postoperative, +/- 3 days)	
Incision appearance: Standard digital photo of the incision (taken by the subject, family member, friend, or caregiver). Subject will submit this photo to the site.
 
VAS (Incision Healing Assessment Form) will be completed based on photo of incision.

Day 14 (+/- 7 days)	
Incision appearance: Physician exam; VAS (Incision Healing Assessment Form); Drainage amount; Assessment of complications; Assessment of return to OR; Assessment of need for antibiotics.
 
(If the subject will not be returning 2 weeks postoperatively as standard of care, they will be asked to take another standardized digital image at 2 weeks, and the 2 week follow-up will be done over the phone.)

Day 35 (+/-14 days)	
Incision appearance: Physician exam; VAS (Incision Healing Assessment Form); Drainage amount; Assessment of complications; Assessment of return to OR; Assessment of need for antibiotics.
 
Functionality and Patient's QoL Assessment (SF12)

Study Completion	Reason for Study Completion

ADVERSE EVENTS

All adverse events reported spontaneously by the patient or in response to questioning or observation by the Investigator will be recorded.

ETHICS/IRB APPROVAL

Before the start of the trial the Investigator will submit the trial to the local independent Ethics Committee/Institutional Review Board (IRB) for review and approval.

PATIENT CONSENT

Before being recruited to the clinical trial, the patient must have given written informed consent to participate.

REFERENCES

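### Does the plan need a rule for which incision counts, and which subgroup applies, in patients having bilateral surgery?

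*Combined protocol and SAP*

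**What the plan says.** Under Assigning Patients to Treatment, the patient is the unit allocated: "The patient will be randomized to the application of either PICO or standard postsurgical dressings". Allocation is 1:1, "PICO versus standard postsurgical dressings, taken from a pre-assigned randomization table". The only sentence on bilateral surgery follows: "If a patient is having a bilateral procedure, they will receive the same dressing treatment on both sides". The Number of Patients section counts the same unit: "1000 patients will be enrolled into the evaluation".

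Elsewhere the text speaks of one incision. The Day 7 row of the Treatment Regime calls for a "Standard digital photo of the incision (taken by the subject, family member, friend, or caregiver"), and the VAS form is scored from that photo. At Day 14 and Day 35 the VAS goes with a physician examination. A subject-taken image replaces the two-week visit only for subjects who do not return then.

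Evaluation Design states the strata: "Patients will be stratified according to the type of surgical procedure (KA/THA) and primary or revision procedure". Data Analysis compares the arms overall, in primary procedures and in revisions, for example "Compare Revision JA PICO vs. SOC incision appearance VAS and drainage amount using t-Test". The tests do not name patient or incision as the unit. On blinding, Evaluation Design says that the appearance of the dressings is something "which will be impossible to blind to both the investigator and/or patient".

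**The concern.** A bilateral patient yields two correlated VAS scores and two drainage amounts in the same arm, while the t-test and chi-square test assume independent observations. Three things are left unsaid.

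- **Which value enters.** It could be one side, the mean of the two, or whichever side is photographed. The study is open label, so a side picked at the time is picked with the dressing known. If the pick leaned one way under PICO and the other way under standard care, the primary VAS comparison would be biased.
- **Whether both sides enter as separate observations.** If they did, the standard error would be too small.
- **Where a mixed patient goes.** Someone with one primary and one revision joint, or one knee and one hip, fits no single level of a stratification factor. In the first case the patient also fits no single subgroup comparison.

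At stake is the type I error of the primary comparison and, to a lesser degree, the make-up of the Primary and Revision subgroups.

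**Working it through.** **Inputs.** From the documents: 1000 patients, allocated 1:1, so 500 per arm. Assumed, because the documents do not give them: bilateral share b, within-patient correlation r between sides (0.3 to 0.9), a two-sided 5% level, normal scores and complete data. The plan gives no derivation of the 1000, so there is no figure of its own to reproduce. Scores are in SD units. The standard error of the arm difference is sqrt(1/500 + 1/500) = sqrt(4/1000) = 0.063 SD.

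**1. One value per patient, same rule in both arms.** Simulation with no treatment effect (1000 patients, 20,000 runs, Monte Carlo error about 0.15 points):

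| b, r | Patient mean | Random side | Better side, both arms |
|---|---|---|---|
| 2%, 0.5 | 5.1% | 5.0% | 5.0% |
| 5%, 0.5 | 5.2% | 5.1% | 5.0% |
| 5%, 0.7 | 5.0% | 5.0% | 5.0% |
| 10%, 0.7 | 4.9% | 4.9% | 4.8% |

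Every rule holds the level.

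**2. What the mean gains over a single side.** With the mean, the average variance per patient is (1 − b) + b(1 + r)/2, against 1 with one side. At b = 5%, r = 0.3 this is 0.95 + 0.05 × 0.65 = 0.9825. The single-side standard error is then larger by 1/sqrt(0.9825) = 1.009, or 0.9%. At r = 0.9 the variance is 0.9975 and the difference is 0.1%. Little precision depends on the choice.

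**3. Both sides entered as independent.** The variance is understated by the factor 1 + 2br/(1 + b), and the true error is 2[1 − Φ(1.96/sqrt(factor))]. At b = 5%, r = 0.5 the factor is 1 + 0.05/1.05 = 1.048 and the error 5.5%. Over r = 0.3 to 0.9:

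- b = 2%: 5.1–5.4%
- b = 5%: 5.3–6.0%
- b = 10%: 5.6–6.9%

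**4. Side chosen differently by arm.** The better of two sides exceeds their mean by sqrt((1 − r)/π) SD on average. Always taking it in one arm, with no selection in the other, gives a bias of b·sqrt((1 − r)/π). Taking the better side in one arm and the worse in the other doubles this. At b = 5%, r = 0.3 the doubled bias is 2 × 0.05 × sqrt(0.7/π) = 0.047 SD, which is 0.047/0.063 = 0.75 standard errors. Over r = 0.3 to 0.9:

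| b | Error, one arm selected | Error, opposite selection |
|---|---|---|
| 2% | 5.0–5.3% | 5.1–6.0% |
| 5% | 5.2–6.6% | 5.9–11.6% |

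These are upper bounds, because every bilateral patient is assumed to be selected. They grow with b. Selection in one arm at r = 0.5 gives about 10% at b = 10% and 24% at b = 20%. Opposite selection at b = 10%, r = 0.7 gives 16.4%.

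**5. Mixed patients.** The overall comparison includes them wherever they are placed. Stratified allocation needs a stratum before the dressing is assigned, so the placement need not depend on the arm. The same placement can then define the subgroup.

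**The case for a change.** The strongest case for a change is that the gap touches the primary outcome in an open-label trial, where the week 1 image comes from the subject or someone close to them. One value per patient may be the obvious reading, but it does not say which value. The bilateral share is unknown, and at 10–20% arm-dependent selection would be far from negligible. An unrecorded side cannot be recovered later, while a written rule costs a few sentences.

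Part of this stands. The rule is absent, and the smallness of the effect depends on a share that the documents do not give. But knowing the dressing is not enough to produce bias: both sides of a patient carry the same dressing, so the choice of side would have to follow a different habit in each arm, and nothing in the documents points to one. The self-taken image is standard only at week 1. At weeks 2 and 5 a physician normally examines the patient. An unblinded examiner could also favour a side, but again it would have to be a different side by arm. The healing form is only described in Appendix 2, so a side field or one form per incision cannot be ruled out. A lost side costs little, since a single side chosen without regard to arm still gives a valid comparison.

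A written rule would also be partly preference. Classing any revision as Revision and then averaging the sides, for instance, puts a primary incision's score into the Revision comparison. It would need further clauses for a knee-plus-hip patient and for a patient with one side missing.

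**Conclusion.** No change to the plan is needed. The silence is real, but it is missing detail and does not lead to a wrong result under the natural reading. Randomization and enrolment are both by patient, and an analyst would take one value per patient, apply the same rule in both arms, count a complication once per patient and keep each mixed patient in the stratum used at allocation. Under any such rule for the VAS the t-test keeps its level, and choosing one side over the mean costs at most 0.9% in standard error at a 5% bilateral share.

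The larger error rates belong to conduct or readings that the documents do not support. Double counting gives up to 6.0% at a 5% share, and opposite selection in every bilateral patient gives up to 11.6%. All these figures rest on an assumed share, a correlation of 0.3 to 0.9, a two-sided 5% level, normal scores and 1000 complete patients. If the share proved near 20% and the side had been chosen freely, the question would deserve a second look when the results are read.

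### The SF-12 is collected before surgery and at Day 35 but has no stated outcome role or analysis; name its scores as secondary outcomes and compare them by ANCOVA on baseline.

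*Combined protocol and SAP*

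**What the plan says.** All references are to the combined protocol and SAP.

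- **Treatment Regime, Pre-Trial row:** "Patient functionality and QoL (quality of life) assessment (SF12". The Day 0 row repeats it as a fallback, "if not done at Pre-Trial visit", and lists it ahead of the operation.
- **Treatment Regime, Day 35 row (window of 14 days either side):** "Functionality and Patient's QoL Assessment (SF12".
- **Primary Objective and Secondary Objectives:** the primary measure is incision appearance by VAS. The secondary measures are drainage, user-friendliness, complications, return to the operating room and antibiotic need. The SF-12 is in neither list.
- **Data Analysis:** the t-test goes to two measures only, "Compare TOTAL PICO vs. SOC incision appearance VAS and drainage amount using t-Test". The rest fall under "Compare TOTAL PICO vs. SOC for all other outcome measures using chi-square based on number in each category". Both rules are repeated for primary and for revision procedures. The last line is "Post-hoc assessment of risk factors – ASA level, surgeon, BMI". No line uses a baseline value of any kind.
- **Number of Patients:** "1000 patients will be enrolled into the evaluation", allocated 1:1.
- **Evaluation Design:** patients are stratified by procedure (KA or THA) and by primary or revision surgery.

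**The concern.** The trial asks each patient for the same instrument twice and then does not say what the answers are for. The background section counts reduced function among the consequences of the complications that the device is meant to prevent, and the SF-12 is the only measure of function or quality of life in the schedule. Its role, its scoring and its analysis should therefore be fixed before the data are seen.

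Two readings are open, and both leave a gap. If the catch-all rule covers the SF-12, someone must choose categories that the plan does not define, and the baseline score has no use. If it does not, the choice of score, cut-point and test is left until after the data are in. Either way, a null result could reflect an inefficient analysis and a positive one could be put down to a late choice.

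**Working it through.** **Inputs from the documents.** 1000 patients at 1:1, so n = 500 per arm if all are followed. SF-12 before surgery and at Day 35.

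**Inputs the documents do not give, assumed here.** Two-sided 0.05; no loss to follow-up; a normally distributed SF-12 score; a true difference d of 0.15 SD (0.20 SD as a second case); correlation r between baseline and Day 35 of 0.2 to 0.6; a median split or quartiles for any chi-square.

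**The plan's own figure.** The 1000 cannot be reproduced, because no alpha, power, effect size or SD accompanies it. For orientation, a two-sided 0.05 t-test with 500 per arm detects (1.960 + 0.842) × sqrt(2/500) = 0.177 SD with 80% power.

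**Unadjusted t-test on the Day 35 score.** SE = sqrt(2/500) = 0.0632 SD. Power = Φ(d/SE − 1.96).
- d = 0.15: d/SE = 2.372; Φ(0.412) = 66%.
- d = 0.20: d/SE = 3.162; Φ(1.202) = 88.5%.

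**ANCOVA on the baseline score.** The SE is multiplied by sqrt(1 − r²), so power = Φ(d/(SE × sqrt(1 − r²)) − 1.96).

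| r | sqrt(1 − r²) | Variance saved against t-test | Power, d = 0.15 | Power, d = 0.20 |
|---|---|---|---|---|
| 0.2 | 0.980 | 4% | 68% | 90% |
| 0.3 | 0.954 | 9% | 70% | 91% |
| 0.4 | 0.917 | 16% | 73% | 93% |
| 0.5 | 0.866 | 25% | 78% | 95% |
| 0.6 | 0.800 | 36% | 84% | 98% |

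**Chi-square, only if the catch-all rule is applied.**
- Median split, d = 0.15: the proportions above the cut are Φ(−0.075) = 0.470 and Φ(0.075) = 0.530. Power = Φ((0.0598 − 1.96 × 0.03162)/0.03157) = Φ(−0.07) = 47%.
- Quartiles, d = 0.15: category probabilities are 0.274, 0.255, 0.243, 0.227 in one arm and the reverse in the other. The noncentrality is 4.82 on 3 df, the critical value is 7.81, and power is 43%.
- At d = 0.20 the two figures are 71% and 69%.

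A simulation of 3000 trials at each of r = 0.3, 0.5 and 0.7 with d = 0.20 agreed: 71-74% for the median-split chi-square, 88-90% for the t-test, and 91%, 96% and 99% for ANCOVA.

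**Where the gain comes from.** At d = 0.15, keeping the score numeric moves power from 43-47% to 66%. Using the baseline then moves it from 66% to between 68% and 84%, depending on r.

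**Covariates for the incision VAS.** If covariates explain a share R² of the variance, adjustment is worth 1000/(1 − R²) − 1000 patients: 1000/0.98 − 1000 = 20 at R² = 0.02, 1000/0.90 − 1000 = 111 at R² = 0.10, and none at R² = 0. The R² values are assumptions. BMI and ASA level are recorded at Day 0. Surgeon appears in no row of the schedule, and the number of surgeons is not given.

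**The case against.** The strongest objection is that the SF-12 is not a listed outcome at all. The catch-all chi-square rule then reads naturally as covering user-friendliness, complications, return to the operating room and antibiotic need, all of which can be counted in categories. This stands. A reader might infer that the plan intends to cut the SF-12 into categories. The documents do not say so and define no cut-point, so the 43-47% figures describe a possible reading and not the plan.

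A second objection also stands. A reader might infer that ANCOVA would be far more precise than any alternative. Against an ordinary t-test on the score, the gain is small at r = 0.2 to 0.3. Low correlations cannot be ruled out, since a joint replacement lies between the two measurements and the follow-up window spans 14 days either side of Day 35.

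Third, a reader might infer that leaving BMI, ASA level and surgeon to a post-hoc look is the same fault. It is not. They are not baseline values of the outcome, an exploratory look at risk factors is legitimate, and an unadjusted t-test in a randomised trial is valid. What remains is an optional gain in precision.

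None of this removes the main point: the SF-12 is collected twice and has no stated role or method.

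**Conclusion.** The point holds as an omission. The SF-12 has no outcome status and no analysis that uses its baseline, under either reading of Data Analysis. At 0.15 SD, ANCOVA adds 2 to 18 percentage points of power over an unadjusted t-test on the score (66% to between 68% and 84%) for r from 0.2 to 0.6. The larger contrast with 43-47% arises only if the catch-all rule is applied with the assumed cut-points. Effect size, correlation, alpha and full follow-up are all assumptions; loss to follow-up would lower every figure.

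The covariate point is minor and depends on an assumed R². No bias is alleged, no stated objective or sample-size statement rests on the SF-12, and the primary VAS comparison is valid as planned.

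**What to change.** 1. In Secondary Objectives, list the SF-12 summary scores as secondary outcomes and define how they are scored.
2. In Data Analysis, compare the Day 35 scores between arms by ANCOVA with the baseline SF-12 score and the stratification factors (KA or THA, primary or revision) as covariates. Report the adjusted difference with a 95% CI. State that the chi-square rule does not apply to the SF-12.
3. As a lesser change, prespecify BMI and ASA level as covariates in the VAS comparison. Add surgeon only if it is recorded and sparse levels are pooled.

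The cost is wording. Items 1 and 2 and the BMI and ASA part of item 3 use data already scheduled, with no new visit or form. Surgeon would need to be confirmed as a recorded item.
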